9. PRE-STUDY AND CONCOMITANT INTERVENTION/MEDICATION

Concomitant medications will be documented during screening and updated during the study. Disallowed medications for this study include: any medication that the investigator feels would be contraindicated in contact lens wear.

Concomitant therapies that are disallowed include: any therapies that the investigator feels would be contraindicated in contact lens wear.

10. DEVIATIONS FROM THE PROTOCOL

Investigator will notify study sponsor upon identification of a protocol deviation. Major protocol deviations must be reported to the sponsor within 24 hours after discovery of the protocol deviation. The Investigator will report deviations per IRB/IEC requirements. All deviations will be tracked and corrective actions implemented as appropriate.

If it becomes necessary for the Investigator to implement a deviation in order to eliminate an immediate hazard to the trial subject, the Investigator may implement the deviation immediately without notification to the sponsor. Within 24 hours after the implemented deviation, the Investigator must notify and provide the rationale to the Sponsor and, as required, the IEC/IRB.

11. STUDY TERMINATION

The occurrence of one or more Unanticipated Serious Adverse Device Effect (USADE), or any SAE where the relationship to study agent cannot be ruled out, may result in stopping further dispensing of test article. In the event of a USADE or SAE, the Sponsor may unmask the treatment regimen for the subject(s) and will discuss this with the Investigator before any further subjects are enrolled.

The Sponsor will determine when a study will be stopped. The Principal Investigator always has the discretion to initiate stopping the study based on patient safety or if information indicates the study's results are compromised.

JJVC reserves the right to terminate the study at any time for any reason. Additionally, the IEC/IRB reserves the right to terminate the study if an unreasonable risk is determined. The study can be terminated by the Principal Investigator at the individual clinical site due to specific clinical observations, if in their opinion, after a discussion with JJVC, it is determined that it would be unwise to continue at the clinical site.

JJVC (and the IEC/IRB and DMC, if applicable) will evaluate all adverse events. If it is determined that an adverse event presents an unreasonable risk, the investigation, or that part of the investigation presenting the risk, will be terminated, as soon as possible.

Should the study be terminated (either prematurely or as scheduled), the Investigator will notify the IEC/IRB and Regulatory Authority as required by local regulatory requirements.

12. PROCEDURE FOR HANDLING PRODUCT QUALITY COMPLAINTS

A Product Quality Complaint (PQC) refers to any written, electronic, or oral communication that alleges deficiencies related to the identity, quality, durability, reliability, safety, effectiveness or performance of test articles after they have been released for clinical trial use.

Potential complaints may come from a variety of sources including but not limited to subjects, clinical research associates (CRA), clinical operations managers (COM), medical monitors, and site personnel, etc. The following are not considered product quality complaints:

- Subject satisfaction inquiries reported via "Subjective Questionnaires" and "Patient Reported Outcomes (PRO)".
- Clinical test articles that are stored improperly or damaged after receipt at the investigational site.
- Lens replacements that occur due to drops/fall-outs.
- Damage deemed by clinicians or clinical staff to be caused by handling by the user, and not indicative of a quality deficiency (i.e., tears, rips, etc.), only in situations where there is no deficiency alleged by the subject.

Within 24 hours of site personnel becoming aware that a PQC has occurred, the PQC must be recorded in the EDC system, which will trigger an automatic email notification to the appropriate COM/CRA and Clinical QA representative. In cases where the EDC system in use is not configured to send automatic notifications or when an EDC system is not used, the COM/CRA is responsible for notifying Clinical QA upon discovery that a PQC has occurred.

Upon receipt of the EDC notification, the COM/CRA will contact the study site to collect additional information which will include:

- Date the complaint was received/recorded in the EDC System (Date of Sponsor Awareness)
- Who received the complaint
- Study number
- Clinical site information (contact name, site ID, telephone number)
- Lot number(s)
- Unique Subject Identifier(s)
- Indication of who first observed complaint (site personnel or subject)
- OD/OS indication, along with whether or not the lens was inserted
- Any related AE number if applicable
- Detailed complaint description (scheduled/unscheduled visit, wear time, symptoms, resolution of symptoms, etc.)
- Eye Care Provider objective (slit lamp) findings if applicable
- Confirmation of product availability for return (and tracking information, if available), or rationale if product is not available for return

Once a complaint is received, it will be assessed by the COM, CRA, or trained site personnel to determine if it is an Adverse Event/Serious Adverse Event (AE/SAE). If the complaint results in an AE/SAE, the COM/CRA, or trained site personnel will follow Section 13 of this protocol. If the AE/SAE was potentially the result of a product quality related deficiency, these procedures also applies and will be executed in parallel.

In some cases, a PQC form may be generated in EDC by the site in error. In this event, the PQC forms will be marked "Intentionally Left Blank" or "ILB". Justification for ILB must be documented.

13. ADVERSE EVENTS

13.1. Definitions and Classifications

Adverse Event (AE) – An AE is "any untoward medical occurrence, unintended disease or injury, or untoward clinical signs (including abnormal laboratory findings) in subjects, users or other persons, whether or not related to the investigational medical device.

Note 1 to entry: This definition includes events related to the investigational medical device or the comparator.

Note 2 to entry: This definition includes events related to the procedures involved. *Note 3* to entry: For users or other persons, this definition is restricted to events related to investigational medical devices."²

An AE includes any condition (including a pre-existing condition) that:

- 1. Was not present prior to the study, but appeared or reappeared following initiation of the study
- 2. Was present prior to the study, but worsened during the study. This would include any condition resulting from concomitant illnesses, reactions to concomitant medications, or progression of disease states
- 3. Pregnancy must be documented as an adverse event and must be reported to the clinical monitor and to the Sponsor immediately upon learning of the event

Serious Adverse Event (SAE) – An SAE is any untoward medical occurrence that:

- Results in death
- Is life threatening
- Requires in-patient hospitalization or prolongation of existing hospitalization
- Results in persistent or significant disability/incapacity (eg, a sight threatening event, a significant persistent or permanent change, impairment, damage, or disruption to the subject's body)
- Is a congenital anomaly/birth defect, or
- Requires intervention to prevent permanent damage (the use of the test article resulting in a condition which requires medical or surgical intervention to preclude permanent impairment of the body structure or a body function). Important medical events that may not result in death, be life-threatening, or require hospitalization may be considered an SAE when, based upon appropriate medical judgment, they may

jeopardize the patient or subject and may require medical or surgical intervention to prevent one of the outcomes listed in the above definition.

Diagnoses and conditions that are considered Ocular Serious Adverse Events include, but not limited to:

- Microbial Keratitis (MK)
- Iritis (including cells in the anterior chamber)
- Permanent decrease in best spectacle corrected visual acuity equivalent to 2 acuity lines or greater
- Central Corneal Opacity
- Central Corneal Neovascularization
- Uveitis
- Endophthalmitis
- Hypopyon
- Hyphemia
- Penetration of Bowman's Membrane
- Persistent Epithelial Defect
- Limbal cell Damage leading to Conjunctivalization

Significant Adverse Events – Those events that are usually symptomatic and warrant discontinuation (temporary or permanent) of the test article (excluding Serious Adverse Events).

Diagnoses and conditions that are considered Ocular Significant Adverse Events include, but not limited to the following:

- Contact Lens Induced Peripheral Ulcer (CLPU)
- Significant Infiltrative Events (SIE)
- Superior Epithelial Arcuate Lesions (SEALs)
- Any Temporary Loss of >2 Lines of BSCVA
- Other Grade 3 or higher corneal findings, such as abrasions or edema
- Non-contact lens related corneal events eg Epidemic Keratoconjunctivitis (EKC)
- Asymptomatic Corneal Scar
- Any corneal event which necessitates temporary lens discontinuation >2 weeks

Non-Significant Adverse Events – Those conditions that are usually asymptomatic and usually do not warrant discontinuation (temporary or permanent) of the test article. However, the Investigator may choose to treat as a precautionary measure.

Diagnoses and conditions that are considered Ocular Non-Significant Adverse Events include, but not limited to the following:

- Non-Significant Infiltrative Event (NSIE)
- Contact Lens Papillary Conjunctivitis (CLPC)
- Superficial Punctate Keratitis (SPK)
- Conjunctivitis: Bacterial, Viral, Allergic

- Blepharitis
- Meibomianitis
- Contact Dermatitis
- Localized Allergic Reactions
- Any corneal event not explicitly defined as serious or significant adverse event, which necessitates temporary lens discontinuation <2 weeks

Adverse Device Effect (ADE) – An ADE is an "adverse event related to the use of an investigational medical device.

Note 1 to entry: This definition includes adverse events resulting from insufficient or inadequate instructions for use, deployment, implantation, installation, or operation, or any malfunction of the investigational medical device.

Note 2 to entry: This definition includes any event resulting from use error or from intentional misuse of the investigational medical device.²

Unanticipated Adverse Device Effect (UADE) – Any serious adverse effect on health or safety or any life-threatening problem or death caused by, or associated with, the test article, if that effect, problem, or death was not previously identified in nature, severity, or degree of incidence in the investigational plan, Investigator's Brochure or protocol, or any other unanticipated serious problem associated with the test article that relates to the rights, safety and welfare of subjects.

13.2. Assessing Adverse Events

In conjunction with the medical monitor, the Investigator will evaluate adverse events to ensure the events are categorized correctly. Elements of categorization will include:

- Seriousness/Classifications (see definition in Section 13.1)
- Causality or Relatedness ie, the relationship between the test article, study treatment or study procedures and the adverse event (not related; unlikely related; possibly related; related see definition in Section 13.2.1)
- Adverse Event Severity Adverse event severity is used to assess the degree of intensity of the adverse event (mild; moderate; severe for all events see definition in Section 13.2.2).
- Outcome not recovered or not resolved, recovering or resolving, recovered or resolved with sequelae, recovered or resolved, death related to adverse event, or unknown.
- Actions Taken none; temporarily discontinued; permanently discontinued; other

13.2.1. Causality Assessment

Causality Assessment – A determination of the relationship between an adverse event and the test article. The test article relationship for each adverse event should be determined by the investigator using these explanations:

• Not Related- An adverse event that is not related to the use of the test article, study treatment or study procedures.

- Unlikely Related An adverse event for which an alternative explanation is more likely, eg concomitant treatment, concomitant disease(s), or the relationship of time suggests that a causal relationship is not likely.
- Possibly Related An adverse event that might be due to the use of the test article, or to the study treatment or study procedures. An alternative explanation, eg, concomitant treatment, concomitant disease(s), is inconclusive. The relationship in time is reasonable. Therefore, the causal relationship cannot be excluded.
- Related An adverse event that is listed as a possible adverse effect (device) or adverse reaction (drug) and cannot be reasonably explained by an alternative explanation, eg, concomitant treatment of concomitant disease(s). The relationship in time is very suggestive, eg, it is confirmed by de-challenge and re-challenge.

13.2.2. Severity Assessment

Severity Assessment – A qualitative assessment of the degree of intensity of an adverse event as determined by the Investigator or reported to him/her by the subject. The assessment of severity is made irrespective of test article, study treatment or study procedure relationship or seriousness of the event and should be evaluated according to the following scale:

- Mild Event is noticeable to the subject, but is easily tolerated and does not interfere with the subject's daily activities
- Moderate Event is bothersome, possible requiring additional therapy, and may interfere with the subject's daily activities
- Severe Event is intolerable, necessitates additional therapy or alteration of therapy and interferes with the subject's daily activities

13.3. Documentation and Follow-Up of Adverse Events

The recording and documenting of adverse events (ocular and non-ocular) begins when the subjects are exposed to the test article, study treatment or study procedure. Adverse events reported before the use of test article, start of study treatment, or study procedures will be recorded as medical history. However, if the condition deteriorates at any time during the study it will be recorded and reported as an AE. Untoward medical events reported after the subject's exit from the study will be recorded as adverse events at the discretion of the Investigator.

Upon finding an adverse event, the Principal Investigator will document the condition in the subject record and in the eCRFs. He/she will complete the Adverse Event /eCRF.

Complete descriptions of all adverse events must be available in the subject record. All Adverse Events including local and systemic reactions not meeting the criteria for "serious adverse events" shall be captured on the appropriate case report form or electronic data system. All adverse events occurring while the subject is enrolled in the study must be documented appropriately regardless of relationship.

It is the Investigator's responsibility to maintain documentation of each reported adverse event. All adverse events will be followed in accordance with applicable licensing requirements. Such documentation will include the following:

• Adverse event (diagnosis not symptom)

- Drawings or photographs (where appropriate) that detail the finding (eg, size, location, and depth, etc.)
- Date the clinical site was notified
- Date and time of onset
- Date and time of resolution
- Adverse event classification, severity, and relationship to test articles, as applicable
- Treatment regimen instituted, including concomitant medications prescribed, in accordance with applicable licensing requirements
- Any referral to another health care provider if needed
- Outcome, ocular damage (if any)
- Likely etiology
- Best corrected visual acuity at the discovery of the event and upon conclusion of the event

In addition, if an infiltrate(s) is present, he/she will complete the Corneal Infiltrate Assessment eCRF. Where necessary, a culture of the corneal lesion will be collected to determine if the infection is microbial in nature. If cultures are collected, the date of culture collection and laboratory utilized will be recorded.

Changes in the severity of an AE shall be documented to allow an assessment of the duration of the event at each level of intensity to be performed. Adverse events characterized as intermittent require documentation of the onset and duration of each episode. Changes in the assessment of relationship to the Test Article shall also be clearly documented.

Subjects who present with an adverse event shall be followed by the Investigator, within licensure, until all signs and symptoms have returned to pre-treatment status, stabilized, or been satisfactorily resolved. If further treatment beyond licensure is required, the patient will be referred to the appropriate health care provider. The Investigator will use his/her clinical judgment as to whether or not a subject reporting with an adverse event will continue in the study. If a subject is discontinued from the study, it will be the responsibility of the Investigator to record the reason for discontinuation. The Investigator will also document the adverse event appropriately and complete the Adverse Event eCRF. Any subjects with ongoing adverse events related to the test article, study treatment or study procedures, as of the final study visit date, should be followed to resolution of the adverse event or until referral to an appropriate health care provider, as recommended by the Investigator. Non-ocular adverse events that are not related to the test article, study treatment, or study procedures may be recorded as "ongoing" without further follow-up.

13.4. Reporting Adverse Events

The Investigator will notify the Sponsor of an adverse event by e-mail, facsimile, or telephone as soon as possible and no later than 24 hours from discovery for any serious /significant adverse events, and 2 days from discovery for any non-significant adverse event. In addition, a written report will be submitted by the Principal Investigator to the IEC/IRB according to

their requirements (Section 13.4.2). The report will comment whether or not the adverse event was considered to be related to the test article, study treatment or study procedures.

13.4.1. Reporting Adverse Events to Sponsor

Serious/Significant Adverse Events

The Investigator will inform the sponsor of all serious/significant adverse events occurring during the study period as soon as possible by e-mail, fax, or telephone, but no later than 24 hours following discovery of the event. The Investigator is obligated to pursue and obtain information requested by the Sponsor in addition to that information reported on the eCRF. All subjects experiencing a serious/significant adverse event must be followed up and all outcomes must be reported.

When medically necessary, the Investigator may break the randomization code to determine the identity of the treatment that the subject received. The Sponsor and study monitor should be notified prior to unmasking the test articles.

In the event of a serious/significant adverse event, the Investigator must:

- Notify the Sponsor immediately
- Obtain and maintain in the subject's records all pertinent medical information and medical judgment for colleagues who assisted in the treatment and follow-up of the subject
- Provide the Sponsor with a complete case history which includes a statement as to whether the event was or was not related to the use of the test article
- Notify the IEC/IRB as required by the IEC/IRB reporting procedure according to national regulations

Unanticipated (Serious) Adverse Device Effect (UADE)

In the event of an Unanticipated (Serious) Adverse Device Effect (UADE), the Investigator will submit a report of the UADE to the Sponsor and IEC/IRB as soon as possible, but no later than 24 hours after the Investigator first learns of the effect. This report is in addition to the immediate notification mentioned above.

The Sponsor must conduct an evaluation of the UADE and must report the results of the evaluation to FDA, the IEC/IRB and participating Investigators within 10 working days after the Sponsor first receives notification of the effect.

Non-Serious Adverse Events

All non-serious adverse events, including non-serious adverse device effects, will be reported to the sponsor by the Investigator no later than 2 days from discovery.

13.4.2. Reporting Adverse Events to the Responsible IEC/IRB and Health Authorities

Adverse events that meet the IEC/IRB requirements for reporting must be reported within the IEC/IRB's written guidelines. Each clinical site will refer to and follow any guidelines set forth by their Approving IEC/IRB. Each clinical site will refer to and follow any guidelines set forth by their local governing Health Authorities.

The Sponsor will report applicable Adverse Events to the local health authorities according the written guidelines, including reporting timelines.

13.4.3. Event of Special Interest

None.

13.5. Reporting of Pregnancy

Subjects reporting pregnancy (by self-report) during the course of the study will be discontinued after the event is recorded as an Adverse Event. Once discontinued, pregnant participants and their fetuses will not be monitored for study related purposes.

At the Investigator's discretion, the study participant may be followed by the Investigator through delivery. However, this data will not be collected as part of the clinical study database. Pregnant participants are not discontinued from contact lens or solution related studies for safety concerns, but due to general concerns relating to pregnancy and contact lens use. Specifically, pregnant women are discontinued due to fluctuations in refractive error and/or visual acuity that occur secondary to systemic hormonal changes, and not due to unforeseen health risks to the mother or fetus.

14. STATISTICAL METHODS

14.1. General Considerations

All data summaries and statistical analyses will be performed using the SAS software Version 9.4 (SAS Institute, Cary, NC). Throughout the analysis of data, the results for each subject/eye will be used when available for summarization and statistical analysis. Unscheduled visits will be summarized separately and will be excluded from the statistical analysis.

Summary tables (descriptive statistics and/or frequency tables) will be provided for all baseline variables, efficacy variables and safety variables as appropriate. Continuous variables will be summarized with descriptive statistics (n, mean, standard deviation [SD], median, minimum and maximum). Frequency count and percentage of subjects or eyes within each category will be provided for categorical data.

All statistical analysis will be conducted on the per-protocol population defined in Section 14.3.

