2.6	Bare Eye Corneal Topography	Collect 3 corneal topography maps over the subject's bare eye (OD only).		
2.7	Bare Eye Wavefront Aberrometry	Collect wavefront aberration measures 3 times over the subject's bare eye with Distance (4 m) and Near (25 cm) targets (OD only).		

Visit 2: Lens Fitting				
Step	Procedure	Details		
2.8	Lens Selection	Select the contact lens power based on subjective best sphere refraction.		
2.9	Lens Insertion	The subject or the investigator will insert the study lenses. Record the time of lens insertion. Check for lens damage under the slit lamp before proceeding with lens settling. Replace damaged lenses if applicable.		
2.10	Lens Settling	Allow the study lenses to settle for a minimum of 10 minutes.		
2.11	Subjective Lens Fit Assessment	 Evaluate overall lens fit acceptance (acceptable or unacceptable) based on centration, movement and other fitting characteristics. An unacceptable fit is deemed by one of the following criteria: limbal exposure at primary gaze or with extreme eye movement; edge lift; excessive movement in primary and up gaze; or insufficient movement in all three of the following conditions: primary gaze, up gaze, and Josephson push up. Note: if lens fit is unacceptable subject will be 		
2.12	Over the Lens Distance and	discontinued from the study. Record the subject's distance and near visual acuity to the nearest letter with the study lenses		
2.13	Subjective Best-Sphere Over-refraction	Perform subjective best-sphere refraction over the study lenses with a phoropter (adopt the maximum plus to maximum visual acuity (MPMVA) approach and use the duo-chrome test for binocular balancing) and record the best corrected distance visual acuity to the nearest letter (OD, OS, OU). Note : The endpoint criterion for the duo-chrome test is the lens power at which the red and green sides of the chart appear to be equally distinct.		

Step Procedure Details However, if the subject's response changes from "red" to "green" with only a 0.25 D change in power and no report that the two sides appear to be equally sharp, the refraction endpoint should be the lens power that leave the red chart sharper. 2.14 Lens Power Modification (if applicable) The subject's best sphere over-refraction cannot be positive (>0.00 D) or, in the case of a myopic over-refraction, it cannot be -0.50 D or higher	Visit 2: Lens Fitting				

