The final evaluation will ordinarily take place immediately following the last scheduled follow-up visit per the study protocol. It may also take place at any point the subject discontinues the study or is terminated from the study.

Final Evaluation			
Step	Procedure	Details	
F.1	Final Exam Form	Indicate if the subject completed the study successfully. If subject discontinued from the study indicate the reason.	
F.2	Subjective spherocylindrical Refraction	Perform bare-eye subjective spherocylindrical refraction with a phoropter and record the best corrected distance visual acuity to the nearest letter (OD, OS, OU).	
F.3	Exit Slit Lamp Biomicroscopy	FDA Slit Lamp Classification Scale will be used to grade the findings. If the clearance of the fluorescein needs to be expedited, preservative-free rewetting drops may be instilled.	

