8. SUBJECTS COMPLETION/WITHDRAWAL

8.1. Completion Criteria

Subjects are considered to have completed the study if they:

- provided informed consent;
- are eligible;
- completed all visits through the final visit

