14.3. Analysis Populations

Safety Population:

All subjects who are administered any test article excluding subjects who drop out prior to administering any test article. At least one observation should be recorded.

Per-Protocol Population:

All subjects who have successfully completed all visits and did not substantially deviate from the protocol as determined by the trial cohort review committee prior to database hard lock (Per-Protocol Population). Justification of excluding subjects with protocol deviations in the per-protocol population set will be documented in a memo to file.

Intent-to-Treat (ITT) Population:

All randomized subjects regardless of actual treatment and subsequent withdrawal from study or deviation from protocol. At least one observation should be recorded.

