14.7. Other Exploratory Analyses

Summary statistical analysis will be provided for the following other observations:

- Corneal and test article on-eye topography
- Accommodative response with target vergence of 0.25 D, 1 D, 2 D, 3 D and 4 D
- Slit lamp findings (OD, OS)
- LogMAR visual acuity under HLHC, LLHC, and HLLC conditions (OD, OU)
- Lens fit assessment (OD, OS)
- Subjective vision assessment (CLUE Vision)

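### The dropout sensitivity analysis in 14.9 has no analysis set that can support it, and on the likelier reading the per-protocol rule in 14.1 also leaves fit failures out of the lens-fit table

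*Combined protocol and SAP*

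**What the plan says.** Section 14.1 gives one rule for the analysis set: "All statistical analysis will be conducted on the per-protocol population defined in Section 14.3". Section 14.3 defines per-protocol as "All subjects who have successfully completed all visits and did not substantially deviate from the protocol". It also defines a Safety set, limited to subjects given a test article, and an ITT set, limited to randomized subjects. No analysis is assigned to either.

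Section 14.9 expects dropout to be a main source of missing data. It plans a sensitivity analysis by multiple imputation if dropout exceeds 15%. It does not say which set is used, or whether the proportion is pooled or by arm.

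For lens fit, the note to Step 2.11 in 7.2 says "if lens fit is unacceptable subject will be" discontinued. Step F.1 of the Final Evaluation reads "Indicate if the subject completed the study successfully. If subject discontinued from the study indicate the reason". Section 14.7 states "Summary statistical analysis will be provided for the following other observations" and lists lens fit for both eyes, naming no set.

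Two other passages bear on the reading. Section 14.1 separates summaries from analysis in one place: "Unscheduled visits will be summarized separately and will be excluded from the statistical analysis". Section 8.1 counts as completers those consented, eligible subjects who "completed all visits through the final visit", while 8.2 asks that discontinued subjects finish the visit they are in.

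**The concern.** A sensitivity analysis for dropout has to include the subjects who dropped out, and to inform the RMY-100 minus OK contrast it has to include both arms. If no defined set does both, the only planned check on missing data cannot do its job when triggered. Under the 14.1 default it would run on completers, where it can fill isolated missing readings but says nothing about those who left.

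Lens fit raises a related question. If an unacceptable fit leads to discontinuation, and discontinued subjects are outside per-protocol, the overall acceptable/unacceptable item can take only one value in the table. According to 14.2 the data will be used to design future trials, so the proportion who cannot be fitted is worth reporting correctly.

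Finally, 13.3 starts adverse-event recording at the first study procedure, but the Safety set is tied to the test article, which Controls never receive.

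**Working it through.** **Set membership, read literally.** Inputs: the definitions in 14.3; 5.1 (not randomized; lens fitted to the Test group at Visit 2 only); 6.1 (no test article for Controls); Step 2.9 (insertion) preceding Step 2.11 (fit assessment).

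| Subject | Safety | Per-protocol | ITT |
|---|---|---|---|
| Test, completes | yes | yes | no |
| Test, unacceptable fit at Step 2.11 | yes | no (if F.1 governs) | no |
| Test, leaves before Visit 2 | no | no | no |
| Control, completes | no | yes | no |
| Control, drops out | no | no | no |

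Per-protocol has both arms but no dropouts. Safety has Test subjects who leave after insertion, but no Controls, so it cannot support a between-arm contrast. ITT is empty.

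**Is the trigger within reach?** Section 4.3 gives about 25 Test subjects enrolled with at least 20 to complete, and about 20 Controls with at least 15 to complete. Loss at the minimums = (enrolled − minimum completing) / enrolled:

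- Test: (25 − 20)/25 = 20.0%
- Control: (20 − 15)/20 = 25.0%
- Pooled: (45 − 35)/45 = 22.2%

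All exceed 15%. The smallest counts that cross it are 4/25 = 16.0% in Test (3/25 = 12.0% does not), 4/20 = 20.0% in Control (3/20 = 15.0% is not greater than 15%) and 7/45 = 15.6% pooled (6/45 = 13.3% does not). At the minimums, the per-protocol set would have at most 35 subjects. A set of all enrolled eligible subjects with at least one measurement could have up to 45.

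**Lens fit.** The documents give no fit-failure rate. As an assumption, take 1 to 5 failing Test subjects, all 25 fitted, none replaced, and a subject failing if either eye fails. Acceptance among all fitted = (25 − failures)/25, which runs from 24/25 = 96% to 20/25 = 80%. A completers-only table shows 100% throughout. At 3 failures, with exact (Clopper-Pearson) 95% intervals:

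- all fitted: 22/25 = 88% (68.8 to 97.5)
- completers only: 22/22 = 100% (84.6 to 100)

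If 8.2 led to replacement of all three, the figures would be 25/28 = 89.3% (71.8 to 97.7) against 25/25 (86.3 to 100). Subjects who left before Visit 2 would reduce the number fitted.

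**Safety.** With about 20 Controls among 45 planned subjects, 20/45 = 44.4% are outside the Safety set.

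**The case against.** The strongest reply concerns lens fit. Section 14.1 says that each subject's or eye's results will be used when available, for summaries as well as analysis, and it mentions summary tables apart from the per-protocol sentence. A reader could take the fit table as a summary not bound to per-protocol. Under 8.1 and 8.2, a subject who fails fitting but finishes Visit 2 might also be called a completer. This stands as real doubt. Against it, 14.7 calls its own output statistical analysis and F.1 treats successful completion and discontinuation as alternatives, so exclusion is the likelier reading but not a certain one. If the table is only a summary, no set is named for it.

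A reader might go further and infer that the plan conceals the fit-failure rate. The documents do not support that. F.1 records every reason for discontinuation, 14.9 puts counts of missing values in tables and listings, and the Safety set already holds the fit failures. What is missing is the assignment of that set to the table.

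It may also be said that ITT obviously meant enrolled subjects. Probably so, but 14.9 would still not name it, and 14.1 would still send the analysis to per-protocol.

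Control adverse events are not lost either: 13.3 requires all events during enrolment to be documented. Only a reporting set is missing.

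One might want fit failures left out of the 15% count. I would not propose it. With 3 fit failures and 4 other dropouts, the pooled proportion would fall from 7/45 = 15.6% to 4/42 = 9.5%, so the check would run less often, and the choice is one of preference.

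**Conclusion.** The dropout limb holds on the text. No set in 14.3 contains both arms together with the dropouts, so the 14.9 analysis cannot serve its purpose as written, and the plan's own enrolment allowance (20% to 25%) exceeds its 15% trigger. Those percentages are allowances, not forecasts, and the empty ITT set rests on taking the word randomized literally.

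The lens-fit limb holds on the likelier reading only, and its size rests on an assumed number of failures.

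A reader might infer that the primary RMY-100 minus OK estimate is biased. The documents do not show that: the planned primary model is assigned to per-protocol, and nothing planned uses ITT or Safety. Nor do they establish that fit failures can never contribute an on-eye wavefront reading at Step 2.16, because 8.2 asks discontinued subjects to complete the current visit. No planned primary efficacy estimate is shown to change. In an exploratory pilot the point is minor.

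**What to change.** - **14.3 and 14.9.** Redefine ITT as all enrolled eligible subjects in either arm with at least one measurement. Name it in 14.9, as a stated exception to 14.1, as the set for the dropout sensitivity analysis, reported beside the per-protocol model.
- **14.7.** Summarise lens fit on all Test subjects fitted with a lens, which is the existing Safety set, including those discontinued at Step 2.11. Report the number of unacceptable fits.
- **Adverse events.** Report them by arm for all subjects who undergo any study procedure, in line with 13.3.
- **14.3 with 8.1, 8.2 and F.1.** Reconcile these on whether a discontinuation at Step 2.11 counts as successful completion.

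The cost is wording and a few extra tables. No new measurements are needed: fit is recorded at Step 2.11, and the Final Evaluation is completed for discontinued subjects. The fit summary may look less favourable than a completers-only table.
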